The MR image analysis will be carried out at the Vascular Image Lab, directed by Drs. [name] and [name], in Department of Radiology at the University of Washington. The original MRI examination identification (ID) number, image date/time, and series information will be replaced with a new and randomly generated MRI analysis ID number. A master log file containing both original and new image information, and study subject ID, will be generated at the time of renaming. This blinding process will ensure that MRI reviewers are fully blinded to patient information and time sequence during the image analysis. It will also protect patient confidentiality in accordance to HIPAA guidelines.

Prior to image review, all cross-sectional images from TOF, T1, PD, T2, and post-CE T1 weightings will be co-registered using the carotid bifurcation as a physical landmark.

2. Visual Assessment of Atherosclerotic Lesion Type

A previously published MRI-based AHA lesion classification scheme will be used for this evaluation: type I-II = near-normal wall thickness; type III = diffuse wall thickening or small eccentric plaque; type IV-V = plaque with a necrotic core; type VI = complex plaque with a possible surface defect, hemorrhage, or thrombus; type VII = calcified plaque; and type VIII = fibrotic plaque without a necrotic core.

3. Quantitative Measurements of Plaque Volume and Tissue Composition

(a) Plaque Volume Measurement: Contours will be placed around the lumen and outer-wall boundaries of carotid artery. These contours may be created manually or automatically. The arterial wall area = outer-wall area – lumen area. The wall volume will be calculated as: wall area x 2 mm (slice thickness). Wall/outer wall ratio will be used as a normalized wall index that is adjusted for differences in carotid artery size in the common carotid, bifurcation, and internal carotid arteries.

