A carotid ultrasound sub-study for assessment of carotid intima media thickness (CIMT) has been added to this study protocol as a sub-study. If the patient agrees after reviewing the informed consent, the carotid ultrasound exams will take place on the same date as the carotid MR scans: baseline, C12, C24 and C36 post randomization.

[figure not shown]
All ultrasound scans will be done using the SonoSite Micromaxx System (Bothell, WA) and equipped with a 10.0 Mhz transducer. This system was used in the ARBITER-2/3 and 6 studies. B-mode scans of the right and left common carotid arteries, carotid bulbs and internal carotid arteries will be performed as illustrated in the follow-up figure. Any plaque or wall thickness > 1.5 mm will be identified using both oblique and cross-sectional views and recorded using a carotid artery map for location. Then, common

carotid arteries and carotid bulbs will be focused on IMT scans using both anterior and lateral angles to cover about 60% of the carotid wall. A digital cine-loop of each vessel will be recorded digitally. The images will be transferred and stored onto CDs at the

Coronary Atherosclerosis Research Lab.

CIMT measurements will occur on desktop computers (Dell 2.4 GHz, Pentium 4, 1 GB RAM) using an automated IMT detection program by SonoSite. The CIMT of the 10mm adjacent segment distal to the carotid bulb of the far wall of the common carotid artery at both anterior and lateral angles of both the right and left side will be measured from 4-6 representative images with automated IMT detection and the mean CIMT will be reported. A carotid IMT example is shown below. Both the sonographer and person performing the IMT measurement will be blinded to the treatment group. Inter-observer and intra-observer variability will be determined on a subset of cases and reported for the automated CIMT analysis.

Cardiology fellows, for example, [name] [name], performed the carotid ultrasound exams and IMT measurements as their research projects.

E. Study Documentations

E.1. Regulatory Documents

(1) Grant Application and Sponsor Communications – including the original grant, award notifications, study communications with NHLBI and industry supporters, and study progress reports.

(2) IRB Binder – including the IRB applications and modifications, both submitted materials and approved documents. Each of the study sites has a site-specific IRB binder.

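### The CIMT sub-study defines its measurement site in contradictory terms and states reader masking to treatment only, which leaves within-arm CIMT change open to visit-order bias

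*Combined protocol and SAP*

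**What the plan says.** All of the CIMT method is under the heading Ultrasound Examination at the end of section D.

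- **Timing.** For consenting participants, "the carotid ultrasound exams will take place on the same date as the carotid MR scans: baseline, C12, C24 and C36 post randomization".
- **Vessels.** B-mode scans of the right and left "common carotid arteries, carotid bulbs and internal carotid arteries will be performed as illustrated in the follow-up figure". The text then narrows to IMT imaging: the common "carotid arteries and carotid bulbs will be focused on IMT scans using both anterior and lateral angles".
- **Site.** The quantity measured is "The CIMT of the 10mm adjacent segment distal to the carotid bulb of the far wall of the common carotid artery", at both angles and on both sides.
- **Reading.** CIMT is "measured from 4-6 representative images with automated IMT detection and the mean CIMT will be reported". Cardiology fellows are said to have done both the examinations and the measurements.
- **Masking.** "Both the sonographer and person performing the IMT measurement will be blinded to the treatment group". Nothing is said about scan date or visit order.
- **Reproducibility.** "Inter-observer and intra-observer variability will be determined on a subset of cases and reported for the automated CIMT analysis".

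The MRI readings are handled differently. A.3 masks them to time sequence, treatment, lipid levels and clinical course. D.3, item 1, replaces examination ID, date and series information with a random code so that "MRI reviewers are fully blinded to patient information and time sequence during the image analysis". D.3, item 3, adds a commonly covered region and the same reviewers for all images.

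**The concern.** There are two separate weaknesses, and both bear on the comparison of one visit with another.

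The first is the landmark. A 10 mm window is reproducible over three years only if every reader places it against the same anatomical point. This one is described by two terms that exclude each other. If the window were placed differently at different visits, part of any recorded change would be a difference between two pieces of wall. If such misplacement is unrelated to arm, it adds noise to every CIMT comparison; if it drifts with time, it also adds a false change within arms.

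The second is visit order. The reading depends on which 4-6 images count as representative, and no selection rule is given. All three arms receive active lipid therapy and are expected to improve. A reader who knows which loop is the baseline could, without intent, favour thicker frames early and thinner frames late. That would look like regression in every arm.

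**Working it through.** **Site.** Set the terms side by side:

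1. The section lists common carotid, bulb and internal carotid as three sites.
2. Going distally, the common carotid ends at the bulb and the internal carotid lies beyond it.
3. Distal to the bulb therefore means internal carotid, while the same sentence says common carotid. Both cannot hold.
4. IMT imaging is focused on the common carotids and bulbs. Read literally, distal to the bulb points outside that target. This favours a wording slip for the part of the common carotid that adjoins the bulb.

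**Masking.** MRI readers: treatment and time sequence, with a recoding procedure. CIMT sonographer and reader: treatment only, with no recoding, reading order or rule for matching the window across visits.

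**What a visit-order shift would do.** The plan has no CIMT sample size, effect, SD or test, so there is no figure to reproduce. The following is an illustration. None of its inputs is a CIMT figure from the documents.

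- Participants per arm: 180 / 3 = 60, as if every planned completer joined. The sub-study is optional, so the true number may be smaller.
- SD of the individual change: 0.10 mm (assumed).
- True change: zero in both arms compared.
- Reading shift b between first and last visit: 0 to -0.03 mm (assumed), the same in both arms because the reader is masked to treatment.

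Standard error of a within-arm mean change: 0.10 / √60 = 0.0129 mm. The shift in standard-error units is b / 0.0129, that is 0.78, 1.55 and 2.33 for 0.01, 0.02 and 0.03 mm.

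Expected between-arm difference: (0 + b) - (0 + b) = 0, whatever b is.

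Simulation, 4,000 runs for each shift, two-sided 5% tests:

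| Shift b (mm) | Mean within-arm change (mm) | Within-arm paired test rejects | Between-arm test rejects |
|---|---|---|---|
| 0 | -0.000 | 5.3% | 5.2% |
| -0.01 | -0.010 | 11.5% | 4.4% |
| -0.02 | -0.020 | 32.3% | 5.0% |
| -0.03 | -0.030 | 61.2% | 4.8% |

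The simulation standard error at 5% is √(0.05 × 0.95 / 4000) = 0.34 percentage points, so the between-arm column is compatible with 5% throughout. The mean between-arm difference stayed within 0.0005 mm of zero.

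**The case against.** The case for leaving this alone has real substance.

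- **The intended site is fairly clear.** The sentence names the common carotid far wall, and IMT imaging is focused on common carotids and bulbs. The section refers to a scanning figure and an IMT example that we cannot see, and E.1 lists a binder with sub-study protocols and a procedure manual. This stands: misplacement is a possibility, not a finding. The sentence would still need correcting.
- **Silence is not disclosure.** A reader might infer that CIMT readers know visit order. The documents do not say so; they only fail to mask it. Nor do they say who picks the images. A sonographer at a live scan could hardly be masked to visit, so the point concerns the offline reader.
- **There are safeguards.** Automated edge detection, averaging over images, angles and sides, and the variability check all help. They do not answer the point: edge detection acts after the frames are chosen, and agreement on a subset does not reveal a shift tied to visit order.
- **The randomized comparison is not biased.** A reader might infer that the CIMT treatment effect is compromised. With treatment masking, a shift common to the arms cancels, as shown above. The reservation is that the trial is open-label (A.2), so this protection depends on the treatment masking working.
- **CIMT is peripheral.** It is not among the endpoints in A.3, and F.3 gives it no analysis; the paired t tests there are for primary and secondary endpoints. Change over time is the natural use of four repeated scans, but it is not a stated CIMT analysis.

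Two further inferences lack support. One is that the literal segment would be absent from the images: the internal carotids are also scanned. The other is that misplacement would swamp the treatment effect: no figure in the documents allows that to be judged.

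**Conclusion.** The point holds in a limited form. The CIMT site is defined by terms that cannot both be true, and the stated masking falls short of the standard this protocol sets for its MRI readings. What is exposed is within-arm CIMT change, and only if the offline reader knows scan order. The primary and secondary MRI endpoints are untouched.

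The size cannot be taken from the documents. The 12% to 61% rejection rates rest wholly on the assumed SD, shift and arm size; they show the direction and the mechanism, not an estimate of bias in this trial. The change is worth making because it is cheap, but the matter is confined to an optional sub-study.

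**What to change.** 1. Establish from the sub-study records and stored images which segment was actually read. Then restate it with a single landmark. If confirmed, this would be the far wall of the common carotid over the 10 mm immediately proximal to the bulb. Use the same landmark at all four visits.
2. Replace examination IDs and dates on the stored loops with random codes, on the model of D.3, item 1. Have the offline reader, not the live sonographer, read each participant's loops in random order, blind to visit and treatment, including when choosing the 4-6 images.
3. Where loops have already been read without masking to order, either re-read them or report within-arm CIMT change with that limitation stated.

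The cost is one corrected sentence, a recoding step, and a wait until a participant's loops are complete. Re-reading could be the larger item: the text describes the fellows' measurements in the past tense, so some readings probably exist. The loops are also held at the Coronary Atherosclerosis Research Lab, while the MRI recoding is described for the Vascular Imaging Lab, so the procedure would have to be set up for ultrasound.

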Official Title: Carotid Plaque Composition by Magnetic Resonance Imaging During Lipid Lowering Therapy

NCT00715273

Study Protocol and Statistical Analysis Plan - 06APR2016

This final protocol version reflects the extension of clinical events monitoring and open-label study as supported by American Heart Association and Alpha Phi grants.

Responsible Party:

Principal Investigator

[name] [[name]]

Professor

University of Washington, Seattle, WA, USA

Study Protocol and Procedures (April 2016)

Study Title: CAROTID PLAQUE COMPOSITION BY MRI DURING LIPID-
LOWERING, supported by NHLBI (R01 HLO63895)

Short title: CPC

A. Study Protocol

A.1. Study Objectives/Aims:

(1) To test the primary hypothesis that intensive lipid therapy decreases carotid plaque lipid content assessed by CE-MRI. To achieve this goal, we will (a) perform carotid CE-MRI scans for all 180 study subjects at baseline, 1, 2, and 3 years; (b) perform quantitative assessments of plaque lipid content; (c) compare the plaque lipid content between pre- and post-treatment for all 3 therapy groups; (d) demonstrate the time-course of plaque lipid content change during intensive lipid modification over 3 years by assessing serial carotid CE-MRI examinations.

(2) To test the secondary and exploratory hypotheses that intensive lipid therapy is associated with plaque regression and decreased plaque enhancement assessed by CE-MRI. To achieve this goal, we will (a) perform quantitative assessments of plaque volume and enhancement; (b) compare the plaque volume and enhancement between pre- and post-treatment for all 3 therapy groups; (c) examine the relationship between plaque lipid and volume and enhancement characteristics; (d) demonstrate the time-course of plaque volume and enhancement change during intensive lipid modification over 3 years.

(3) To examine the association of factors including clinical risk factors, lipids, lipoprotein heterogeneity, inflammatory markers, oxidative stress markers and carotid plaque characteristics (lipid, volume, and enhancement). To achieve this goal, we will (a) perform laboratory testing on lipids, lipoprotein heterogeneity, inflammatory markers, oxidative stress markers at baseline and on therapy; (b) describe the change in each of these measurements between baseline and on treatment; (c) determine the statistical significance of each measured risk variable and its change in relation to the change in plaque characteristics.

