Step 3. Registration: After manual boundary detection, the CASCADE Program will automatically identify and outline the lumen and wall boundary of the carotid artery in the remaining 4 sequences. An example is shown in Figure 3 below. Expert readers will review the outlines generated by CASCADE, and have the opportunity to manually override errors in the automated outlines that may occur as a result of marginal image quality or flow artifact.

Step 4. Auto-segmentation: The CASCADE Program will automatically identify and quantify the tissue component within the arterial wall. Expert readers will then review the output of CASCADE to insure correct classification of the plaque components. An example is shown in Figure 4 below with loose matrix in purple and lipid content in yellow.

The image analysis for this study will be performed at the time of completing both MRI examinations. By doing so, a region of each carotid artery, covered by both baseline and 2-year scans, will be identified and image analysis will be performed within the region. This will allow the same reviewers to analyze all images and therefore to reduce the inter-reader variability. The analysis will be performed at Vascular Imaging Lab using CASCADE with automated tissue segmentation capability using MEPPS.

(c) Plaque Tissue Composition: This will be calculated based on each identified tissue volume and wall volume at each given location: tissue volume/wall volume x (100%), and presented as percentage.

(d) Summary of Plaque Variables: CASCADE can produce a list of comprehensive plaque assessments. Plaque burden measurements will include the carotid lumen, wall, and outer-wall area in mm², wall thickness in mm, and wall/outer-wall ratio (a normalized wall index that is adjusted for carotid artery size difference) that is equivalent to the % of atheroma area used in the coronary intravascular studies. The plaque tissue characteristics will be presented as absolute measurement in mm² and as a proportion of the corresponding vessel wall area, expressed as in % lipid, % loose matrix, % calcium, % fibrous tissue and % hemorrhage. Additionally, the plaque integrity will also be evaluated and described as ruptured, thin or thick fibrous cap, with and without ulceration, with and without thrombus.

[figure not shown]

Ultrasound Examination:

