1. Descriptive Statistics: Prior to more formal analysis we will explore the data to detect outliers or other distribution problems and display the data in graphical and tabular format using histograms, boxplots, scatterplots, frequency listings for dichotomous and categorical variables and descriptive statistics for all patients and subcategories of patients. We will also calculate the various outcome measures, such as percent lipid in the carotid arterial wall, as a mean per MRI slice, in order to control for the varying number of MRI slices per subject. Throughout the analyses we will take account of potential differences in MRI measurements due to the effect of scan platform or study site. The site effect is a difference among measurements that cannot be explained away by subject characteristics, such as age and gender or study site. We can formally test for a site effect, describe its magnitude and adjust for it using random effects models. Similarly, the platform (fixed) effect can be addressed by using a dummy variable for the platform. The site and platform effects are confounded (because groups of sites use one of the two platforms). Even so, the site effect can be addressed by a model that nests the sites within platform.

2. Difference between baseline and 3 years: Differences of primary and secondary endpoints between baseline and 3 years after intensive lipid-lowering therapy will be compared using paired 2-tailed t tests to determine the significance. A multivariate analysis will be performed based on a logistic regression model with plaque lipid composition as the dependent variable to detect the independent patient or therapy variables that are predictive of plaque lipid composition change over a 3-year interval.

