3. Treatment effect with different lipid therapies: This set of analyses addresses the primary and secondary endpoints of determining the treatment effect on lipid composition, plaque wall volume and wall thickness. The simplest form of this analysis will be a t-test or nonparametric Mann-Whitney test comparing the two treatment groups on the change in an outcome variable between baseline and the 3-year MRI assessment. In order to control for important covariates, we will carry out multivariate linear regression, with the 3-year change in the outcome, such as percent of wall volume that is lipid-rich necrotic core, being the dependent variable and independent variables of treatment group (dichotomous). We will also evaluate baseline value of the outcome variable, and any other variables that need to be controlled, such as age and gender. We can also test for an interaction between variables in affecting the outcome by using an interaction term in the model. We will not automatically test all possible interactions. If main effects are included in a final regression model, it would be natural to test to see if there is an interaction between some of the main effects. Choice of which interactions to try will be driven by biological plausibility. For example, if treatment and baseline lipid composition are important and statistically significant main effects in a model, it would be natural to test to see if their interaction is also important. In general, quite large sample sizes are needed to detect interactions, unless they are very strong. However, the sign and magnitude and even marginal statistical significance of an interaction are informative, even if the interaction term is not ultimately included in the model. This comment on use of statistical interaction terms applies to the regression analyses for all of our aims. We routinely carry out statistical diagnostics on these analyses, such as examining residuals.

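### F.3.2 names a logistic model for plaque lipid composition, but the plan defines no binary outcome for that model

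*Combined protocol and SAP*

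**What the plan says.** F.3.2 first compares baseline with 3 years by paired t tests. It then adds a predictor analysis: "A multivariate analysis will be performed based on a logistic regression model with plaque lipid composition as the dependent variable". The stated purpose is to find patient or therapy variables that are "predictive of plaque lipid composition change over a 3-year interval". Aim 3(c) in A.1 has the same kind of target: "determine the statistical significance of each measured risk variable and its change in relation to the change in plaque characteristics".

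The outcome is defined elsewhere. D.3, item 3(c), computes tissue composition as "tissue volume/wall volume x (100%), and presented as percentage". D.3, item 3(d), also reports tissue characteristics in mm². F.3.1 summarises the outcome per subject as "percent lipid in the carotid arterial wall, as a mean per MRI slice".

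F.3.3 analyses the same quantity differently: "we will carry out multivariate linear regression, with the 3-year change in the outcome".

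**The concern.** An ordinary logistic model needs a yes/no outcome (or ordered categories, in its extended form). Percent lipid is neither, and nothing in the plan turns it or its change into one. Someone must therefore add a rule before the analysis can be run, and nothing in the plan requires that rule to be set before the data are seen.

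At stake is which variables F.3.2 reports as independent predictors of lipid change. Because the sentence covers therapy variables as well as patient variables, a therapy verdict taken from this particular model would depend on the added rule too.

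**Working it through.** **1. Is there a binary outcome anywhere?** The places that bear on it are:

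| Place | Treatment of plaque lipid |
|---|---|
| D.3 item 3(c) | percentage of wall volume: continuous |
| D.3 item 3(d) | mm² and percent of wall area: continuous |
| F.3.1 | mean percent per slice: continuous |
| F.3.2, opening sentence | paired t test: continuous |
| F.3.3 | t test or Mann-Whitney, and linear regression of 3-year change: continuous or ranked |
| F.3.5 | Pearson or Spearman correlation: continuous or ranked |
| F.3.2, predictor sentence | logistic regression: needs categories |

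The categorical plaque variables in D.3 (AHA lesion type, cap status, ulceration, thrombus) are separate gradings that F.3.2 does not name. The only other logistic regression, in F.3.4, is for cardiovascular events, which are naturally binary.

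**2. What the model would need.** A logistic model is logit P(Y = 1) = a + b·x, with Y equal to 0 or 1. The change in percent lipid is D = (3-year value) − (baseline value), which can be negative, zero or positive. To use it, one must set Y = 1 if D ≤ c. The plan states neither c nor how D = 0 is classed.

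**3. How much the verdict depends on c.** The plan has no figure of its own to reproduce here. Inputs: n = 180 and r = 0.18 from F.3.5; two-sided 5%. Assumptions: one normal predictor with correlation r with D, D normal, and a Wald test. For each simulated trial, D was cut at its sample median and, separately, at its lower quartile. The share of trials in which one cut gives significance and the other does not is:

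| r | Verdicts differ |
|---|---|
| 0.05 | about 10% |
| 0.10 | about 19% |
| 0.18 | about 31% |
| 0.25 | about 25% |
| 0.30 | about 14% |

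Repeat simulations moved these by no more than about 1.5 percentage points. The figure peaks at middling power, so 31% is near the maximum and not typical of all effects. At r = 0.18 it runs from 29% to 37% if D is uniform, logistic, t with 5 degrees of freedom, or Laplace.

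**4. If c were chosen after seeing the data to minimise p.** For one predictor with no effect (r = 0), the false-positive rate is about 5% with the median fixed, 12% for the best of three cuts (25th, 50th and 75th percentiles), and 18% for the best of seven (20th to 80th in steps of 10). Exact zeros reduce this: with 20%, 40% or 60% of patients at zero change, the seven-cut rate is 17%, 13% or 8%.

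**5. Secondary illustration: the level taken literally.** Suppose a fractional logit is fitted to the 3-year level without baseline. Take a variable correlated 0.2 with baseline percent lipid that has no effect on change given baseline, and a between-scan correlation of 0.8. Both values are assumptions. The implied correlation with the 3-year level is 0.2 × 0.8 = 0.16. By Fisher z, power = Φ(√177 × atanh 0.16 − 1.96) = Φ(0.187) = 57%; simulation gives about 55%. So the variable is flagged in over half of trials, against about 5% for linear regression of change adjusted for baseline. The range is 12% to 95% for variable correlations of 0.1 to 0.3 and between-scan correlations of 0.6 to 0.9.

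**The case against.** **The level is only loose wording.** The section heading, its opening sentence and the stated purpose all concern the difference over 3 years, so the intended outcome is very likely the change. This stands, and it makes the level-without-baseline reading unlikely: that reading also needs a fractional logit that the plan never names, and neglect of the baseline value that F.3.3 says it will evaluate. But the defect remains, because a logistic model of change still lacks its cut.

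**The goal is covered elsewhere.** F.3.3 gives a linear model of the 3-year change with covariates, and F.3.5 extends correlations with plaque change to models with several variables. This largely stands. No aim rests on the faulty sentence alone, and that lowers the severity.

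**The cut-shopping rates assume conduct that the plan does not describe.** This is correct. The plan does not propose choosing a cut by its p-value; it only fails to rule it out. The disagreement in step 3 needs no such conduct, since both cuts are fixed.

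**Dichotomising must lose power.** A reader might infer this, but the documents give no distribution for the change. At r = 0.18, linear regression has about 68% power in these simulations. A median split has 48% if change is normal, 29% if uniform and 81% if Laplace, so the direction is not settled and no general loss is claimed.

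**Conclusion.** The F.3.2 sentence is wrong as written: it pairs a logistic model with an outcome defined only on continuous scales. If the change is dichotomised, two reasonable fixed cuts disagree about a predictor in roughly 10% to 31% of trials for r between 0.05 and 0.30. This assumes n = 180, normally distributed change and a single predictor. The documents give no cut, SD, distribution or between-scan correlation, so the sizes are conditional; the textual defect is not.

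A reader might infer that the trial's treatment comparison is compromised. The documents do not support that. The paired t tests, the F.3.3 comparison of treatments and the F.3.5 correlations do not use this model. Only a therapy term read from the F.3.2 model itself would be affected. This is a low-severity correction to a supplementary analysis.

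**What to change.** In F.3.2, change the model and outcome to: multiple linear regression with the 3-year change in percent lipid (mean per slice) as the outcome, adjusted for baseline percent lipid. This matches the model type and outcome of F.3.3. The site and platform adjustment needs no new promise, since F.3.1 already says: "Throughout the analyses we will take account of potential differences in MRI measurements due to the effect of scan platform or study site".

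If a binary outcome was intended, state the cut-point and how zero change is classed before the data are seen.

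The cost is one sentence in the analysis plan, with no new data.
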